### 3.2.3 Inclusion Criteria

**Subjects must meet all of the following criteria at the time of randomization:**

1. Has completed the written informed consent and assent process
2. Is age  $\geq 12$  years and  $\leq 17$  years on Study Day 0

3. Agrees to stay in contact with the study site for the duration of the study, provide updated contact information as necessary, and has no current plans to move from the study area for the duration of the study
4. For female subjects: agrees to avoid pregnancy from 28 days prior to Study Day 0 and for the full duration of the study. Women physically capable of pregnancy (not sterilized and still menstruating or within 1 year of the last menses) in sexual relationships with men must use an acceptable method of avoiding pregnancy during this period. Acceptable methods of avoiding pregnancy include a sterile sexual partner, sexual abstinence (not engaging in sexual intercourse), hormonal contraceptives (oral, injection, transdermal patch, or implant), vaginal ring, intrauterine device (IUD), or the combination of a condom or diaphragm with spermicide
5. Has general good health, confirmed by medical history and physical examination
6. Had BCG vaccination at least 5 years ago documented through medical history or by presence of healed BCG scar
7. Tests QFT-GIT negative at screening, using the manufacturer's recommended threshold of 0.35 IU/mL

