### 5.3. MODIFIED INTENT-TO-TREAT ANALYSIS SET

The Modified Intent-to-treat analysis set is defined as all participants included in the Safety analysis set who had a negative QFT-GIT test result at Day 84.

A participant will be programmatically included in the Modified Intent-to-treat analysis set if the participant:

- Is included in the Safety analysis set.
- AND
- Has a negative QFT-GIT test result at the Day 84 visit.

For analyses and presentations based on the Modified Intent-to-treat analysis set, participants will be analyzed according to the treatment assigned regardless of the treatment received.

The Modified Intent-to-treat analysis set will be used for efficacy analyses.

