## 5.5. PER PROTOCOL ANALYSIS SET

The Per Protocol analysis set is defined as all participants in the Modified Intent-to-treat analysis set who received all relevant doses of BCG, H4: IC31 or Placebo and had no major protocol deviations.

A participant will be included in the Per Protocol analysis set if the participant:

- Is included in the Modified Intent-to-treat analysis set.
- Received all relevant doses, based on the date of study vaccination as recorded on Exposure (Day 0) and Exposure (Day 56) eCRFs:
  - o BCG: Day 0.
  - o H4:IC31 or Placebo: Day 0 and Day 56.
- Did not have any major protocol deviations as recorded on the Protocol Deviation eCRF and agreed with Aeras prior to the relevant unblinding activities of the analysis/study.
- Did not have a treatment deviation as identified in collaboration with the clinical trial manager (CTM) in accordance with the Aeras/QuintilesIMS Process Instruction Treatment Deviation Identification and Authorization document.
- Out-of-window QFT-GIT positive results should not be included in the analysis for the PP analysis set.

Refer to the relevant Blind Data Review (BDR) documentation for additional details.

Document: Aeras\_C-040-404\_SAP\_V2\_0

Author: [name]

Version Number:

2.0

Version Date:

29SEP2017

Template No: CS\_TP\_BS016 – Revision 3

Reference: CS\_WI\_BS005

Effective Date: 01May2012

Copyright © 2012 Quintiles Transnational Corp. All rights reserved.

The contents of this document are confidential and proprietary to Quintiles Transnational Corp. Unauthorized use, disclosure or reproduction is strictly prohibited.

The Per Protocol analysis set will be based on the participant level flag assigned in Appendix 1 of the BDR report, as authorized by Aeras prior to DB lock.

Efficacy analyses will also be performed using the Per Protocol analysis set as a sensitivity analysis.

---

Document: Aeras\_C-040-404\_SAP\_V2\_0

Author: [name]

Version Number:

2.0

Version Date:

29SEP2017

Template No: CS\_TP\_BS016 – Revision 3

Reference: CS\_WI\_BS005

Effective Date: 01May2012

Copyright © 2012 Quintiles Transnational Corp. All rights reserved.

The contents of this document are confidential and proprietary to Quintiles Transnational Corp. Unauthorized use, disclosure or reproduction is strictly prohibited.

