### 14.1.3. DERIVATIONS

Based on the aforementioned, the following variables, as presented in the planned TLF shells, will be derived for post-vaccination visits and/or time points:

- QFT-GIT testing compliance derived per visit:
  - o Yes: QFT-GIT assessment date is within the protocol-defined visit window.
  - o No: QFT-GIT assessment date is outside the protocol-defined visit window.
  - o Missing: The participant is expected to have a QFT-GIT assessment available.
  - o Refer to APPENDIX 8: Protocol-defined Visit Windows for the relevant protocol-defined visit windows.
- QFT-GIT result classification at each visit (use the retest result if available). The Investigator's assessment will be used, which is based on the algorithm below.

QFT-GIT Result Classification	QFT Nil	QFT Ag - QFT Nil	QFT Mitogen - QFT Nil
Positive	≤ 8.0	≥ 0.35 (primary analysis threshold) and ≥ 25% of QFT Nil value	Any
Negative		< 0.35 (primary	≥0.5

Document: Aeras\_C-040-404\_SAP\_V2\_0

Author: [name]

Version Number:

2.0

Version Date:

29SEP2017

Template No: CS\_TP\_BS016 – Revision 3

Reference: CS\_WI\_BS005

Effective Date: 01May2012

Copyright © 2012 Quintiles Transnational Corp. All rights reserved.

The contents of this document are confidential and proprietary to Quintiles Transnational Corp. Unauthorized use, disclosure or reproduction is strictly prohibited.

QFT-GIT Result Classification	QFT Nil	QFT Ag - QFT Nil	QFT Mitogen - QFT Nil
Indeterminate		analysis threshold) OR ≥ 0.35 (primary analysis threshold) and < 25% of QFT Nil value	< 0.5
Indeterminate	> 8.0	Any	Any

- If the QFT-GIT result is indeterminate at any of the visits Day 84, M6, M9, M12, M15, M18, M21, M24, M27 or M30, the QFT-GIT test will be repeated (QUANT2 form in the eCRF used to record the result). If the repeat result is negative or indeterminate, the participant will continue with the study visits as if the participant did not convert, and the result for the corresponding visit will be deemed “negative”.
- Any QFT-GIT conversion status:
  - o The QFT-GIT conversion status is assigned hierarchically in the order provided below:
    - Yes: Participant has at least one positive QFT-GIT result classification, regardless of missing or indeterminate results at any other visit and regardless of at which visit the positive QFT-GIT result is recorded.

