      - Post-Day 84 QFT-GIT conversion: First positive QFT-GIT result classification recorded post-Day 84.
      - Early QFT-GIT conversion: First positive QFT-GIT result classification recorded at Day 84.
    - No: Participant has no positive QFT-GIT result classification and the last available QFT-GIT result classification is negative.
    - Missing: Participant has no positive/negative/indeterminate QFT-GIT result classification available.
- Censored:
  - o Participants who do not experience a primary endpoint or early conversion (early conversion is only applicable to the analyses based on the Randomized analysis set), will be censored at the date of their last available, non-positive QFT-GIT result.
  - o The following SAS code will be implemented for all Kaplan-Meier analyses, where:
 

```
PROC LIFETEST DATA = <>;
    TIME Months*Censored(1);
    TEST Treatment_Group;
RUN;
```

    - Censored = 1 represents censored participant.
    - Censored = 0 represents participant who experienced an event.
    - Months represent the available follow-up time (months) per participant since:
      - Day 84 (applicable to analyses based on the mITT and PP analysis set).
      - Randomization (applicable to analyses based on the Randomized analysis set).
- Event:
  - o Participants who experience a primary endpoint or early conversion will be indicated as having an event (depending on the relevant table, early converters will be included/excluded from the participants experiencing an event).

Document: Aeras\_C-040-404\_SAP\_V2\_0

Author: [name]

Version Number:

2.0

Version Date:

29SEP2017

Template No: CS\_TP\_BS016 – Revision 3

Reference: CS\_WI\_BS005

Effective Date: 01May2012

Copyright © 2012 Quintiles Transnational Corp. All rights reserved.

The contents of this document are confidential and proprietary to Quintiles Transnational Corp. Unauthorized use, disclosure or reproduction is strictly prohibited.

- Available follow-up time (months) until first QFT-GIT conversion:
  - o The number of months of follow-up time will be derived for each participant based on the date of randomization/Day 84 (depending on the relevant table) and either the censor or event date.
  - o 1 month = 4 weeks.
  - o For the sensitivity analysis the follow-up time will be rounded to the nearest 6-month interval for any of the following visits:
    - Month 6.
    - Month 12
    - Month 18.
    - Month 24.

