### 14.3.2. ANALYSIS OF EXPLORATORY EFFICACY ENDPOINT

The following tables will be presented for the Modified Intent-to-treat analysis set:

- QuantiFERON levels (IU/mL) upon and following first positive QFT-GIT result:
  - o Default summary statistics for QFT-GIT results at the following time points:
    - First positive QFT-GIT result:
      - The p-value based on the Mann-Whitney-Wilcoxon test will be used for pair-wise comparisons between treatment groups.
    - 3 months-post first positive QFT-GIT result:
      - Number and percentage (%) of participants with a negative QFT-GIT.
    - 6 months-post first positive QFT-GIT result:
      - Number and percentage (%) of participants with a negative QFT-GIT.
  - o This table is to include all participants with at least one positive post-Day 84 QFT-GIT result.
  - o This table will be repeated for the Per Protocol analysis set.
- First QuantiFERON reversion:
  - o Number of participants with first QFT-GIT negative value within the following categories will be included:
    - Within 3 months post-conversion.
    - Within 6 months post-conversion.
    - At any time during follow-up.
  - o At risk defined as participants with:
    - A primary endpoint.
    - A QFT-GIT result available at the relevant visit within 6 months (for the first two lines) or at any time post-initial conversion (for the third line) after the primary endpoint occurrence.
  - o This table will be repeated for the Per Protocol analysis set.
- Alternative QFT-GIT thresholds:
  - o Number and percentage of participants who EVER experienced the following alternative threshold values (i.e., at any post-Day 84 timepoint):
    - $\geq 0.20$ .
    - $< 0.2$  at any time point prior to conversion and  $> 0.70$  at any time point post-Day 84.
    - $> 0.70$ .
    - $> 4.0$ .
  - o Vaccine efficacy presented:
    - Point estimate (based on the conditional binomial distribution).
    - 95% CI (based on the conditional binomial Clopper-Pearson method with mid-p correction).
  - o This table will be repeated for the Per Protocol analysis set.
- Trends in QFT-GIT sustained conversions and end-of-study reversions:
  - o Number and percentage (%) of participants in each category:
    - Participants who were negative at Month 24 or the Month 24 call-back visit. Percentages (%) will be calculated based on the number of participants with non-missing Month 24 or Month 24 call-back values.

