### 14.3.3. DERIVATIONS

Based on the aforementioned, the following variables, as presented in the planned TLF shells, will be derived for post-vaccination visits and/or time points:

- QFT-GIT result classification (refer to Section 14.1.3: Derivations). Substitute the primary analysis threshold value with the alternative threshold value.
- Available follow-up time (months) until QFT-GIT:
  - o Months represent the available follow-up time (months) per participant since first QFT-GIT conversion.

---

Document: Aeras\_C-040-404\_SAP\_V2\_0

Author: [name]

Version Number:

2.0

Version Date:

29SEP2017

Template No: CS\_TP\_BS016 – Revision 3

Reference: CS\_WI\_BS005

Effective Date: 01May2012

Copyright © 2012 Quintiles Transnational Corp. All rights reserved.

The contents of this document are confidential and proprietary to Quintiles Transnational Corp. Unauthorized use, disclosure or reproduction is strictly prohibited.

- Negative at Month 24:
  - o Participants who are negative at Month 24 or who initially converted at Month 6 or Month 12 and are negative at the  $\geq 24$  Month call-back visit.
- Prevention of conversion OR conversion with reversion:
  - o Participants who are consistently negative OR
  - o Participants who have a negative QFT-GIT value within six months after their initial conversion (i.e., +/-/-, +/+/-, +/-/+, +/m/-, +/-/m).
- Prevention of conversion OR conversion with reversion and non-positive (i.e. negative or missing) QFT-GIT results at six-months post-initial-conversion:
  - o Participants who are consistently negative OR
  - o Participants who have a negative QFT-GIT value at the last available testing timepoint within six months after their initial conversion (i.e., +/-/-, +/+/-, +/m/-, +/-/m).
- Prevention of conversion OR conversion with reversion and non-positive (i.e., negative or missing) QFT-GIT results at the end of the study:
  - o Participants who are consistently negative throughout the study OR
  - o Participants who initially converted at Month 18 or Month 24 (i.e., +/-/-, +/+/-, +/m/-, +/-/m) and later reverted OR
  - o Participants who initially converted at Month 6 or Month 12 and have a call-back Month 24 visit that is negative (i.e., +/-/-/-, +/+/-/-, +/+/+/-, +/-/+/-, +/-/m/-, +/m/-/-, +/m/m/-, +/+/m/-).
- QFT-GIT end of study sustained conversion status:

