  - o Yes: At 3 and 6 months following first QFT-GIT conversion AND at the Month 24 call-back visit (if applicable), QFT-GIT result classifications are derived as positive.
  - o No: At 3 and/or 6 months following first QFT-GIT conversion and/or at the Month 24 call-back visit (if applicable), QFT-GIT result classification is derived as negative.
  - o Missing: None of the aforementioned QFT-GIT result classifications (yes, no) has been assigned at 3 or 6 months post-conversion or at the Month 24 call-back visit, QFT-GIT result classification is derived as missing.
- The confidence interval for VE is calculated using the conditional binomial method (Clopper-Pearson method with mid-p correction) as follows:  
 The number of participants with a conversion ( $n_A$ ) in one of the treatment groups (for example H4:IC31) and the number ( $n_B$ ) of participants with a conversion in another treatment group (for example Placebo), are assumed to have Independent Poisson distributions with rate parameters  $\lambda_A$  and  $\lambda_B$ , respectively, but inference is conditional on the total number of conversions,  $n = n_A + n_B$ . Conditional on  $n$ ,  $n_A$  has a Binomial distribution,  $\text{Bin}(n, \pi)$ , where

$$\pi = \frac{\lambda_A F_A}{\lambda_A F_A + \lambda_B F_B} = \frac{\theta F_A}{\theta F_A + F_B}$$

$\theta = \lambda_A \lambda_B$  and  $F_A$  and  $F_B$  are the total lengths of follow-up across all subjects in the relevant treatment groups (Treatment Group A/Treatment Group B), that is,  $F = \sum (\text{Duration of VE Follow-up Period [Days]})$ .

Document: Aeras\_C-040-404\_SAP\_V2\_0

Author: [name]

Version Number:

2.0

Version Date:

29SEP2017

Template No: CS\_TP\_BS016 – Revision 3

Reference: CS\_WI\_BS005

Effective Date: 01May2012

Copyright © 2012 Quintiles Transnational Corp. All rights reserved.

The contents of this document are confidential and proprietary to Quintiles Transnational Corp. Unauthorized use, disclosure or reproduction is strictly prohibited.

A point estimate and exact two-sides 95% CI ( $\pi_L, \pi_U$ ) for  $\pi$  is then calculated (Clopper - Pearson method with mid-p correction) based on the number of participants with a conversion in one of the treatment groups (for example H4:IC31), relative to the total number of participants  $n = n_A + n_B$  who had at a conversion in either of the two compared treatment groups. The following SAS® code will be used:

```
PROC FREQ DATA = <>;

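### The ≥0.20 row of the alternative-threshold table (SAP 14.3.2) can count participants already at 0.20–0.34 IU/mL at entry as events, so its VE is not clearly a VE for conversion at 0.20

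*SAP*

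**What the plan says.** The alternative-threshold table in SAP 14.3.2 is specified for the mITT set and repeated for Per Protocol. It gives "Number and percentage of participants who EVER experienced the following alternative threshold values (i.e., at any post-Day 84 timepoint"), followed by four rows: ≥0.20; <0.2 before conversion with >0.70 after Day 84; >0.70; and >4.0. Only the second row sets a condition on earlier values. VE uses the conditional binomial method with a mid-p 95% CI.

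Three rules decide who can enter the table:

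- Protocol 3.2.3: "Tests QFT-GIT negative at screening, using the manufacturer's recommended threshold of 0.35 IU/mL".
- SAP 5.3, mITT: "Has a negative QFT-GIT test result at the Day 84 visit". No separate cut-off is given. For classifying results, SAP 14.1.3 says the Investigator's "assessment will be used, which is based on the algorithm below", and that algorithm uses 0.35.
- SAP 5.5, Per Protocol: "Is included in the Modified Intent-to-treat analysis set".

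SAP 14.3.1 states the aim as the effect of alternative thresholds on conversion and reversion rates. The VE method in SAP 14.3.3 starts from "The number of participants with a conversion" in each of two groups.

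Two further rules bear on the row. SAP 14.3.3 says of the result classification: "Substitute the primary analysis threshold value with the alternative threshold value". SAP 14.1.3 defines "Early QFT-GIT conversion: First positive QFT-GIT result classification recorded at Day 84", as distinct from a post-Day 84 conversion.

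**The concern.** The row lowers the event threshold to 0.20, while the population is still defined by being negative at 0.35. That leaves a band from 0.20 to 0.34 in which a participant is negative for entry and positive for the row. I call such participants carriers. The band lies inside the 0.2–0.7 uncertainty zone cited in Protocol 1.1, so it is unlikely to be empty.

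A carrier whose value does not change can be counted as an event. The table exists to show whether VE depends on the threshold. If one row counts people who have not converted and the others do not, a lower VE in that row could be taken for a threshold effect when it comes from the counting rule.

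**Working it through.** The plan gives no figure for this row, so there is none to reproduce. The check is first logical, then an illustration of size.

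**1. Can a non-converter be an event?** Take QFT-Ag minus QFT-Nil = 0.25 at Screening, Day 84 and Month 6.

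- Screening: 0.25 < 0.35, so negative and eligible.
- Day 84: 0.25 < 0.35, so negative and in mITT.
- Month 6: 0.25 ≥ 0.20 after Day 84, so an event in the ≥0.20 row.

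The value never moved.

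**2. Are the other rows affected?** The >0.70 and >4.0 rows are not affected in this way, because mITT participants start below 0.35. The exceptions in SAP 14.1.3 should be rare: a value ≥0.35 but under 25% of Nil, and a repeat indeterminate result deemed negative. The <0.2/>0.70 row has its own prior-value condition.

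**3. Illustration of size.** Inputs:

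- True VE 50%, the design value in Protocol 7.6.
- 300 per arm (assumed; 330 planned) and equal follow-up.
- 40 placebo v 20 vaccine true events. At the protocol's 10% per year, 40/300 = 13.3% corresponds to about 16 months. A second base of 80 v 40 is shown.
- Carrier share 1, 2, 4 or 6%. This is an assumption, since the documents give no figure. It means k = 3, 6, 12 or 18 per arm, equal by arm, all counted and none truly converting.

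Formula: apparent VE = 1 − (v + k)/(p + k), with v vaccine and p placebo events. For k = 18: 1 − 38/58 = 34.5%.

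| k per arm | 3 | 6 | 12 | 18 |
|---|---|---|---|---|
| 40 v 20, all counted | 46.5% | 43.5% | 38.5% | 34.5% |
| 40 v 20, half counted (k/2) | 48.2% | 46.5% | 43.5% | 40.8% |
| 80 v 40, all counted | 48.2% | 46.5% | 43.5% | 40.8% |
| 80 v 40, half counted (k/2) | 49.1% | 48.2% | 46.5% | 44.9% |

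A true VE of 0 stays at 0: 1 − 58/58.

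**4. Precision.** Mid-p 95% CIs at k = 18:

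| Base | Without carriers | With carriers |
|---|---|---|
| 40 v 20 | 15.0 to 71.3% | 1.6 to 56.8% |
| 80 v 40 | 27.2 to 66.1% | 18.3 to 57.4% |

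**5. Unequal carriers.** With 12 in placebo and c = 3, 6, 12 or 18 in vaccine, 1 − (20 + c)/52 = 55.8, 50.0, 38.5 or 26.9%. The row can move either way.

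**The case against.** **The SAP may already exclude these people.** If the substituted threshold in 14.3.3 is carried into the conversion-status rule of 14.1.3, a value of 0.20–0.34 at Day 84 becomes an early conversion and not a post-Day 84 event. This is the best counter-reading, and it could remove Day 84 carriers. But the SAP does not say that it governs a table defined by ever reaching a value. It does not rebuild mITT at 0.20. The 14.3.3 derivations cover post-vaccination visits only, so Screening values are untouched. Two programmers could reach different counts.

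**The row may be deliberate.** One mITT denominator serves all four rows, and SAP version 2.0 revised the prior-value condition while leaving it on one row only. An ever-at-or-above count is a legitimate description. The table shells, which may carry a footnote, are not available. This stands, and it is a reason to keep the row. It does not make the attached VE a VE for conversion.

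**A reader might infer that the row should simply be restricted to participants below 0.20.** The documents do not support that. Someone at 0.25 at Screening and Day 84 and 5.0 at Month 12 meets the primary endpoint and counts in the >0.70 and >4.0 rows. Restriction alone would drop that person from the lowest threshold and leave the rows no longer nested.

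**Restriction does not remove assay noise.** Read the ±0.24 IU/mL in Protocol 1.1 as a 95% range (an assumption; the figure is from a low-burden setting), so SD = 0.24/1.96 = 0.122. A participant stable at 0.10 is below 0.20 at both entry checks with probability 0.629, and at or above 0.20 at least once in four visits with probability 0.605; the product is 38%. For a stable 0.15 it is 0.434 × 0.812 = 35%. If 30 per arm were stable at 0.10 (assumed), 30 × 0.380 = 11.4 noise events would remain, and VE at 40 v 20 would read 1 − 31.4/51.4 = 39%. This objection stands.

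**Conclusion.** The gap is real as the text is written: the ≥0.20 row can count participants who have not converted at 0.20, and the SAP supports more than one count for it.

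The direction of the effect depends on the arms. Similar carrier numbers by arm are supported by randomisation at Screening but are an assumption at Day 84, which is after vaccination. If they are similar, a non-zero VE is pulled toward zero. If they differ, it can move either way.

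The size cannot be estimated from the documents. The 46.5% to 34.5% range rests on assumed carrier shares and on no carrier truly converting. Carriers who do convert are subject to the vaccine effect, so the dilution would then be smaller. A reader might infer a large known bias, or doubt about the primary or secondary results; neither follows. The primary endpoint and the 0.35 secondary analysis use 0.35 throughout, and the alternative-threshold secondary analysis has its own prior-value condition.

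This is minor: one exploratory row and its Per Protocol repeat.

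**What to change.** In SAP 14.3.2:

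1. Keep the existing row on the common mITT denominator, label it 'ever ≥0.20', and report by arm how many were already ≥0.20 at Screening or Day 84.
2. Add one row, 'conversion at 0.20', with at-risk set, denominator and follow-up totals restricted to mITT participants whose QFT-Ag minus QFT-Nil was <0.20 at both Screening and Day 84. Show the number at risk and take VE for conversion at 0.20 from this row. The conditional binomial mid-p method can stay.
3. Footnote that some events in the new row may still reflect assay variability.
4. Repeat for Per Protocol.

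The quantitative values are already collected (SAP 14.1.2), so the work is a few lines of text and minor programming.

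Costs: an extra row; a denominator that differs from the other rows; and loss from the restricted row of participants who start at 0.20–0.34 and later truly convert at 0.35 or above, so that it is not nested with the higher thresholds. It also loses those ≥0.20 at Screening but <0.20 at Day 84 who later cross. It conditions on a Day 84 value, as mITT already does, and noise crossings remain.

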    - Participants who never converted or converted with reversion. Percentages (%) will be calculated based on the number of participants who did not have two missing QFT-GIT values within 6 months of post-initial conversion.

---

Document: Aeras\_C-040-404\_SAP\_V2\_0

Author: [name]

Version Number:

2.0

Version Date:

29SEP2017

Template No: CS\_TP\_BS016 – Revision 3

Reference: CS\_WI\_BS005

Effective Date: 01May2012

Copyright © 2012 Quintiles Transnational Corp. All rights reserved.

The contents of this document are confidential and proprietary to Quintiles Transnational Corp. Unauthorized use, disclosure or reproduction is strictly prohibited.

- Participants who never converted or converted with reversion and have non-positive (i.e., negative or missing) six-month post-initial-conversion QFT-GIT values. Percentages (%) will be calculated based on the number of participants who did not have two missing QFT-GIT values within 6 months of post-initial conversion.
      - Participants who never converted or converted with reversion and have non-positive (i.e., negative or missing) end of study QFT-GIT values. Percentages (%) will be calculated based on the number of participants who did not have the following combination of QFT-GIT values: +/m/m, +/+m/m or +/m/m/m where + = positive and m = missing.
    - o Comparisons of proportions between treatment groups for each category will be performed based on the Pearson chi-square test.
    - o Vaccine efficacy presented:
      - Point estimate (based on the conditional binomial Clopper-Pearson method with mid-p correction).
      - 95% CI (based on the conditional binomial Clopper-Pearson method with mid-p correction).
  - QFT-GIT end of study sustained conversion rates:
    - o Number and percentage (%) of participants in each conversion status category:
      - Yes.
      - No.
      - Missing.
    - o Hazard ratio (H4:IC31/comparator) presented:
      - Point estimates (based on the Cox regression model).
      - P-values for the comparison of the estimated hazard ratios of QFT-GIT end of study sustained conversion based on a one-sided log-rank test.
        - H4:IC31 versus Placebo.
        - BCG versus Placebo.
        - H4:IC31 versus BCG (at the request of the sponsor's partner).
    - o Vaccine efficacy presented:
      - Point estimate (based on the hazard ratio estimate).
      - 80% two-sided CI based on the hazard ratio estimate from the Cox regression model.

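### The exploratory trends table orders vaccine efficacy for four favourable outcomes with a method written for conversions, and never says which event counts.

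*SAP*

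**What the plan says.** The trends table in SAP 14.3.2 has four categories. The first is "Participants who were negative at Month 24 or the Month 24 call-back visit". The second is "Participants who never converted or converted with reversion", and the third and fourth narrow that group by status six months after conversion and at end of study. SAP 14.3.3 derives all four in the favourable direction, as being negative or as prevention of conversion or reversion after it. Each row has its own percentage denominator, set by which QFT-GIT results are missing.

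Two analyses sit under these rows:

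- A test: "Comparisons of proportions between treatment groups for each category will be performed based on the Pearson chi-square test".
- A VE: "Point estimate (based on the conditional binomial Clopper-Pearson method with mid-p correction", and "95% CI (based on the conditional binomial Clopper-Pearson method with mid-p correction".

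The conditional binomial method is defined only in SAP 14.3.3. Its count is "The number of participants with a conversion" in each of two arms. The counts "are assumed to have Independent Poisson distributions with rate parameters", and the terms F_A and F_B "are the total lengths of follow-up across all subjects in the relevant treatment groups". The limit equations give VE as 1 - theta, where theta is the rate ratio. Neither section names the event for the trends table.

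**The concern.** The 14.3.3 method suits the alternative-threshold table earlier in 14.3.2, where the counted event is unfavourable and accrues over follow-up. It was carried over to the trends table without being adapted, and neither written reading gives the intended figure.

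- **Row count as event.** A vaccine that works has more favourable outcomes than placebo. Theta then exceeds 1 and VE is negative.
- **Conversions as event, as 14.3.3 words it.** VE then measures conversion only. It does not use reversion, six-month status or Month 24 status, which are what distinguish the rows. The protocol (2.2, 7.3 and 7.6) names clearance after initial conversion as a possible mechanism; a vaccine acting only that way would show no effect.

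The follow-up terms do not fit either. A status at a visit is a proportion of evaluable participants, and the percentages and Pearson test in the same table treat it so. The VE follow-up period behind F_A and F_B is not defined for such an outcome.

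At stake is a table in which the VE line and the test beside it point in different directions, or in which the VE does not describe its row.

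**Working it through.** The plan gives no numerical figure for this table, so there is none to reproduce. The counts below are assumed for illustration.

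**Inputs.** 310 evaluable per arm; favourable 287 vaccine and 264 placebo (92.6% and 85.2%); equal follow-up, so F_A = F_B. All are assumptions. The method is that of SAP 14.3.3: pi = n_A/(n_A + n_B), mid-p Clopper-Pearson limits for pi, theta = [pi/(1 - pi)] x (F_B/F_A), VE = 1 - theta. (The closing summary formula in 14.3.3 reads without the leading 1 -; I follow the limit equations above it.)

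**1. Row counts as events.**
- pi = 287/551 = 0.521, 95% limits 0.479 to 0.562.
- theta = 287/264 = 1.087, limits 0.920 to 1.285.
- VE = 1 - 1.087 = -8.7%, 95% CI -28.5 to 8.0.
- Pearson chi-square on 287/310 versus 264/310, without continuity correction: 8.63, p = 0.003.

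The test finds a difference in favour of vaccine. The VE has the opposite sign and an interval that spans zero.

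**2. Conversions as events.** Suppose a vaccine leaves conversion unchanged and acts only through reversion. Then n_A = n_B, theta = 1 and VE = 0 with equal follow-up, whatever the difference in reversion.

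**3. Unfavourable complement as event.**
- Counts are 310 - 287 = 23 and 310 - 264 = 46.
- VE = 1 - 23/46 = 50%.
- SAP conditional binomial interval: 18.0 to 70.1, width 52.1 points.
- Risk-ratio (log) interval on the same counts: 19.6 to 68.9, width 49.3 points.
- Ratio of widths: 52.1/49.3 = 1.06.

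**4. Check at the protocol's design values.** Protocol 7.6 assumes 10% per year and a 50% reduction; Table 2-1 plans 330 per arm. I assume exponential conversion over 1.6 years (Day 84 to Day 672), all evaluable, no reversion.
- Favourable, placebo: 330 x exp(-0.10 x 1.6) = 281. Favourable, vaccine: 330 x exp(-0.05 x 1.6) = 305.
- Row counts as events, equal follow-up: VE -8.5% (-27.7 to 7.7); Pearson p = 0.003.
- Row counts with person-time to conversion (F_A/F_B = 1.04): VE -4.4% (-22.8 to 11.2). The undefined follow-up term alone moves the estimate by about 4 points.
- Complement, 25 versus 49: VE 49.0%, 17.9 to 68.9 by the SAP method and 19.4 to 67.7 by risk ratio.

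**5. Range.** I varied conversion over 5% (assumed), 10% and 17% per year (the last from Protocol 7.6), 270 or 330 evaluable per arm, and no reversion or 20% (Protocol 7.6). The row-count VE was negative in every case, from -1.2% to -14.7%.

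**The case against.** The strongest reply is that the sign error depends on one reading. The SAP never says that the favourable count is the event, and the only event it defines is unfavourable. A sensible programmer might use each row's complement without being told and obtain about 50% with a sound interval. The TLF shells, which SAP section 8 says accompany it, may settle the matter and are not available here. This stands as a limit on the claim: a reader might infer that the table will print a negative VE, and the documents do not establish that. It does not remove the point, because the complement is written nowhere in the SAP and both readings that can be taken from the text miss the target.

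Three other inferences also go too far.

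- **That the interval is about three times too wide.** In the 310-per-arm example the SAP interval on the favourable ratio is 36.5 points wide against 12.2 for a risk-ratio interval (-15.0 to -2.8). That ratio ranges from about 2.2 to 4.7 over the scenarios in the working, and it concerns a quantity that should not be reported as VE at all. On the complement the excess is about 6%.
- **That using conversions would give identical VE in all four rows.** The rows have different evaluable denominators, so the converter counts could differ if restricted to them.
- **That this is the main display of late reversion and end-of-study status.** The next table in 14.3.2 gives a Cox-based VE, on an unfavourable event, for end-of-study sustained conversion; other tables and plots cover reversion and positivity patterns.

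**Conclusion.** The point holds as a fault in the written rule for one exploratory table. The SAP orders a VE for four favourable outcomes by a method defined for conversions over person-time and does not name the event. Taken on the row counts, VE for an effective vaccine is negative: -8.7% (-28.5 to 8.0) beside p = 0.003 in the illustration, where the complement gives 50% (18 to 70). Taken on conversions, it does not describe the rows.

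The sizes rest on assumed counts, equal follow-up and a true reduction of about half; the negative sign under the row-count reading does not depend on the particular counts, as long as the vaccine arm has proportionally more favourable outcomes per unit of follow-up. Which reading would be programmed cannot be told from the documents. Primary and secondary VE come from Cox hazard ratios (SAP 14.1.3 and 14.2.3) and are unaffected, as is the adjacent end-of-study sustained conversion table.

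**What to change.** In SAP 14.3.2 or 14.3.3, state for the trends table that VE is 1 minus the ratio, vaccine over comparator, of the risk of the unfavourable outcome complementary to each row. Use that row's stated evaluable denominator in place of F_A and F_B. Name the complement row by row: for the first, positive at Month 24 or at the call-back visit among those with a result.

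A ratio-of-proportions interval, for example score-based, fits this definition and matches the Pearson test. Once the event is corrected it changes the width by only about 6% in the illustration, so it is optional.

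The cost is a few lines of SAP text and a small code change in one exploratory table, with any matching edit to its shell. No new data are needed.
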